9.6 Interim Analyses and Data Monitoring

There are no planned interim analyses for the primary endpoint, the rationale being that this is not a pharmaceutical or device trial that would benefit from standard stopping rules for efficacy. A DSMB will be monitoring the study for safety and study integrity every 6 months.

9.7 Multiple Testing

Two-sided p-values will be reported. When the primary analysis is repeated for each component of the primary endpoint (spirometry referral/completion, new COPD diagnosis, newly prescribed inhaled medication, referral to a respiratory specialist, and pulmonary rehabilitation referral/completion), a Bonferroni correction will be applied to that set of hypothesis tests. Otherwise, no adjustments for multiplicity will be made across analyses of primary and secondary endpoints and other exploratory analyses. Thus, corresponding p-values for these secondary and exploratory outcomes will be interpreted with caution. Confidence intervals will be provided to summarize treatment differences for efficacy end points.

10 Summary of Study Conduct Data

Descriptive summary statistics will be tabulated for baseline patient demographics and clinical characteristics as well as practice characteristics, separately by intervention group and overall. Intervention groups will be characterized as “Basic COPD Education” and “Basic COPD plus CAPTURE Education”. For pooled summaries, “All” will be used as the column heading. All tables will be annotated with the total population size relevant to that table, including any missing observations.

For continuous variables, sample means and standard deviations will be reported. P-values corresponding to two-sample t-tests¹ comparing mean differences between intervention groups will be reported. For categorical variables, number and percentages will be reported (excluding missing values). P-values corresponding to Pearson’s² chi squared statistic or Fisher’s³ Exact test for testing association between categorical predictors and intervention groups, as appropriate, will be given.

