8.1 Primary Objectives

Aim 3: Define the impact of CAPTURE information provided to clinicians in identifying and managing patients with respiratory symptoms (CAPTURE+) across a broad range of primary care settings.

8.2 Practice Behavior in Sites With Vs Without Capture Education and Patient Level Capture Data Provided

Primary Hypothesis 3: Sites where basic COPD and CAPTURE education are provided to clinicians, along with patient level CAPTURE data, will have a higher probability than control sites (i.e., those receiving only basic COPD education) of meeting the composite endpoint in their CAPTURE+ patients within 12 months of baseline.

From medical record review and follow-up patient survey responses, the composite endpoint is met if one of the following is recorded: 1) referral for or completion of clinical spirometry testing, 2) new clinical diagnosis of COPD, 3) newly prescribed respiratory medication (long acting bronchodilator or anti-inflammatory for respiratory condition), 4) referral to a specialist for respiratory evaluation/ treatment, or 5) referral for or completion of pulmonary rehabilitation.

The study will enroll 50 CAPTURE practices and 50 control practices; each practice will enroll 50 patients (for a total of 5,000 patients). We project that within each practice there will be at least five patients previously undiagnosed with COPD who have a CAPTURE+ screening result. The primary analysis will be to compare the average proportion of CAPTURE+ patients per practice that meet the composite endpoint in the two intervention arms. For power and sample size computations, this is a cluster randomized trial of n=50 clusters (practices) per intervention arm with 5 CAPTURE+ patients per cluster (practice). The primary power calculation is based on comparing the average cluster sample proportion (average proportion of CAPTURE+ patients per practice meeting composite endpoint) between intervention arms. Table 5 displays power for a two-sample test comparing average cluster sample proportions, accounting for possible intra-cluster correlation coefficient (ICC) values of 0.05, 0.10 and 0.15 that are typically seen in cluster randomized trials of behavioral interventions

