(<https://www.abdn.ac.uk/hsru/research/research-tools/study-design/>). These calculations assume a type I error of 5% and that the control arm meets the composite endpoint in 5% of CAPTURE+ patients, and the CAPTURE arm meets the composite endpoint in higher percentages (columns of Table 5). There will be variability in the actual number of CAPTURE+ patients per practice. It is standard practice to inflate the number of needed clusters by 12% to account for this extra source of variability. Therefore, our power calculations are based on 44 clusters per intervention arm.

9 General Analysis Considerations

| | | | | | |
|---|-------|------|------|-------|-------|
| Overall power to detect a difference in rate of meeting primary endpoint in CAPTURE group (50 practices/cluster) vs usual care (50 practices/cluster), assuming 5% performance rate in usual care; 50 patients total / practice; assuming 10% prevalence gives 5 CAPTURE+/practice. | | | | | |
| Improvement over usual care | +7.5% | +10% | +15% | +25% | +50% |
| ICC=0.05 | 0.72 | 0.89 | 0.99 | >0.99 | >0.99 |
| ICC=0.10 | 0.65 | 0.84 | 0.98 | >0.99 | >0.99 |
| ICC=0.15 | 0.59 | 0.79 | 0.97 | >0.99 | >0.99 |

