11.1 Primary Efficacy Analysis

The primary efficacy analysis is restricted to CAPTURE+ participants, denoted in section 9.3 as population 1 (Primary Analysis Population). The primary analysis will be to compare the average cluster sample proportion (average proportion of CAPTURE+ patients per practice meeting composite endpoint) between intervention arms. Practices that do not identify any CAPTURE+ subjects will not contribute to this analysis. A two-sample test comparing average cluster sample proportions will be used that explicitly takes into account correlation between individuals treated within the same practice. A two-sided p-value < 0.05 will be considered statistically significant. This analysis corresponds to a generalized estimating equation (GEE)⁴ regression analysis with (1) individual-level binary composite outcome data, (2) CAPTURE intervention group as a covariate, (3) practice id used to identify correlated outcomes, (4) exchangeable correlation matrix that assumes similar correlation between all composite outcome results for patients within the same practice, and (5) an identity link function so that the coefficient parameter corresponding to CAPTURE intervention group represents a difference in outcome probability. The primary analysis would then correspond to a test for whether the CAPTURE intervention group parameter is non-zero.

Technical Details of the Primary Analysis:

This analysis is restricted to CAPTURE+ participants (Primary Analysis Population)

Let $\pi_{ij} = P(\text{Participant } j \text{ from Practice } i \text{ Meets the Primary Endpoint})$.

Let $CAPTURE_i = I(\text{Practice } i \text{ Received Basic COPD plus CAPTURE education intervention})$

Let PRACTICE take on values $i = 1, \dots, 100$ denoting the enrolled practices

For the primary analysis, the GEE model takes the form

$\pi_{ij} = \beta_0 + \beta_1 CAPTURE_i$, where binary outcomes from the same practice are assumed to follow a compound symmetry correlation structure.

R code for the Primary Analysis:

If the R dataset representing CAPTURE+ patients is called **final** and variables are

MetComp=1 if individual met primary (composite) outcome, 0 otherwise

CAPTURE=1 if individual was from a practice randomized to the Basic COPD plus CAPTURE education intervention, 0 otherwise

Practice is a variable with values $1, \dots, 100$ denoting the enrolled practices

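### Holm's step-down would protect the five component tests as well as the planned Bonferroni correction and could detect more: a minor, cheap improvement

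*SAP*

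**What the plan says.** SAP 9.7 (Multiple Testing) opens with "Two-sided p-values will be reported". It then singles out one family, the primary analysis repeated for each component of the composite: "spirometry referral/completion, new COPD diagnosis, newly prescribed inhaled medication, referral to a respiratory specialist, and pulmonary rehabilitation referral/completion". For that family, "a Bonferroni correction will be applied to that set of hypothesis tests". No other analysis is adjusted. The section also promises confidence intervals for efficacy endpoints, without giving their level or saying whether those for the components are adjusted.

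SAP 9.7 gives no family level. The only stated significance level is for the composite, in SAP 11.1: "A two-sided p-value < 0.05 will be considered statistically significant". The components are secondary endpoints (SAP 5.1, Table 1). Protocol 9.1.2.2 describes the secondary practice-behavior analyses as exploratory and leaves them out of the formal power calculation. Neither document mentions Holm or gives a reason for choosing Bonferroni.

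**The concern.** A participant meets the composite through any one component, so a spirometry referral alone is enough. The component tests are the planned way to see whether a positive composite reflects diagnosis and treatment or mainly test ordering. They are also the only family for which the SAP chose to control multiplicity.

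Plain Bonferroni holds every component to 0.01 however strong the evidence on the others. Holm relaxes the threshold step by step once the clearest component has been rejected, and keeps the same familywise guarantee. If the intervention moves several components, some power on the weaker ones is given up without any gain in error control.

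**Working it through.** **Inputs from the documents.** Five two-sided tests (SAP 9.7). Family level 0.05, borrowed from SAP 11.1 as an assumption. Planning figures for the composite (SAP 8.2): "our power calculations are based on 44 clusters per intervention arm", 5 CAPTURE+ patients per practice, a 5% control rate, and "intra-cluster correlation coefficient (ICC) values of 0.05, 0.10 and 0.15".

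**Not in the documents.** Component control rates, component effects, and the correlation between component tests. These are assumed below and varied.

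**Step 1: reproduce the plan's power figures.** Effective patients per arm = 44 × 5 / (1 + 4 × ICC). At ICC 0.10 this is 220/1.4 = 157.1. A pooled two-proportion test at two-sided 0.05 gives:

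| ICC | +7.5% (stated) | +10% (stated) | +15% (stated) |
|---|---|---|---|
| 0.05 | 0.721 (0.72) | 0.894 (0.89) | 0.993 (0.99) |
| 0.10 | 0.654 (0.65) | 0.843 (0.84) | 0.983 (0.98) |
| 0.15 | 0.596 (0.59) | 0.793 (0.79) | 0.968 (0.97) |

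The plan's figures for the composite reproduce.

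**Step 2: thresholds.** Bonferroni uses 0.05/5 = 0.01 for every test. Holm orders the p-values from smallest to largest and compares them in turn with 0.05/5, 0.05/4, 0.05/3, 0.05/2 and 0.05/1, that is 0.01, 0.0125, 0.0167, 0.025 and 0.05, stopping at the first failure. No Holm threshold is below 0.01, so any p-value at or below 0.01 is rejected by both methods.

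**Step 3: cost of the 0.01 level.** With 80% power at two-sided 0.05, the test statistic has mean 1.960 + 0.842 = 2.802. At two-sided 0.01 the critical value is 2.576, so power is Φ(2.802 − 2.576) = Φ(0.226) = 0.59.

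**Step 4: Holm against Bonferroni.** Simulation of 400,000 draws per scenario: five equally correlated normal statistics, correlation 0, 0.3 and 0.6, mean 2.802 for affected components and 0 for the rest.

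| Components truly affected | Bonferroni, power per affected component | Holm | Gain (points) |
|---|---|---|---|
| 1 | 59% | 59% | about 0 |
| 2 | 59% | 61% | about 2 |
| 3 | 59% | 63% | about 4 |
| 4 | 59% | 65–66% | 6–7 |
| 5 | 59% | 68–70% | 9–11 |

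- In every draw, Holm rejected everything that Bonferroni rejected.
- The chance of detecting at least one real effect differed by less than 0.2 points throughout, because the first step is 0.01 in both methods.
- If all five are affected, the chance of showing all five rises from 7% to 29% at correlation 0, 17% to 41% at 0.3 and 28% to 51% at 0.6. This is the best case for Holm.
- Simulated familywise error was at most 0.049 for both methods.

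**Step 5: the plan's composite inputs as a stand-in for each component.** At ICC 0.10 and +10%, the unpooled standard error is √[(0.05 × 0.95 + 0.15 × 0.85)/157.1] = 0.0334, so the mean statistic is 0.10/0.0334 = 3.00. Power at 0.01 is Φ(3.00 − 2.576) = 0.66. Holm gives 0.66, 0.68, 0.70–0.71, 0.72–0.74 and 0.76–0.78 for one to five affected components. With all five affected, 0.42 becomes about 0.50 at +7.5%, and 0.94 becomes 0.97–0.98 at +15%. The pattern matches Step 4.

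**The case against.** The strongest reply is that nothing here is wrong. Bonferroni is valid under any dependence, pre-specified and easy to report. That stands: the point is about efficiency.

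A reader might go further and infer that real component effects will be missed for no benefit. The documents do not support that, for three reasons.

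- **Whether effects will be missed depends on unknowns.** The gain depends mainly on how many components are truly affected, and no component effects are given. If the intervention changes only spirometry ordering, Holm gains essentially nothing. That the components lie on one care pathway does not settle how many will move. Nor does correlation between the tests help: the per-component gain with all five affected falls from about 11 points at correlation 0 to about 9 at 0.6.
- **Bonferroni does have a benefit.** It yields simple simultaneous intervals (99% for each of five) that agree with its tests. Holm has no equally simple counterpart. Against this, SAP 9.7 promises intervals without promising simultaneous ones, so the plan as written does not use that advantage.
- **The stakes are limited.** These are secondary tests that the protocol calls exploratory. The composite is tested alone at 0.05 and is untouched, and estimates with intervals will be reported whichever adjustment is used.

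These replies limit the importance of the point. They do not give a reason to prefer Bonferroni for the tests themselves, since Holm cannot lose a finding that Bonferroni would make.

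**Conclusion.** The point holds as a minor, cheap improvement; the plan contains no error here. For the same familywise control, Holm rejects at least as much as Bonferroni. Its gain in average power per affected component runs from about 0 to 9–11 points on a base of 59%, according to whether one or all five components are affected. There is essentially no change in the chance of finding at least one effect.

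The ordering of the two methods is mathematical and needs no trial-specific assumption. The sizes rest on a family level of 0.05, 80% unadjusted power per affected component, equal effects among affected components, and test correlation between 0 and 0.6. With the plan's composite inputs standing in for each component, the largest gains are about 8, 12 and 4 points at +7.5%, +10% and +15%. The conclusion on the primary endpoint and the sample size do not depend on this choice.

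**What to change.** In SAP 9.7, replace the Bonferroni correction for the five component tests with a Holm step-down adjustment at familywise two-sided 0.05. Stating the level also fills the gap that the section gives none. Add a sentence saying that the component confidence intervals are not adjusted for multiplicity, so that readers do not expect them to agree with the adjusted tests.

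The cost is one phrase, one sentence and a changed option in the code. No new data are needed and the primary analysis stays as it is. The one real loss is the simple set of matching simultaneous intervals, which the SAP does not commit to. SAP 9.2 requires decisions to be documented before unblinding and database lock, so the change belongs before that point. If the sponsor does want simultaneous intervals for the components, keeping Bonferroni and saying so would be a reasonable alternative.

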The clinical trial component (Aim 3) of the CAPTURE study is a cluster-randomized trial of 100 primary care practices affiliated with seven practice-based research networks (PBRNs). Randomization to one of two interventions takes place at the practice level. Both interventions provide clinicians in participating practices with basic COPD education (enhanced usual care). Clinicians from practices randomized to the CAPTURE intervention additionally receive an educational module (CAPTURE education) on the CAPTURE tool. Each of the 100 practices is expected to enroll 50 patients (5000 total patients). In a single visit, each enrolled patient participant completes CAPTURE screening, pre- and post-bronchodilator spirometry and completes demographic, and general and respiratory related health questionnaires. Practices randomized to the CAPTURE intervention are provided with patient-level CAPTURE tool results for the patients it has enrolled in the study. One-year follow-up chart reviews and participant surveys are used for a pre-identified subset of participants to assess whether CAPTURE screening and sharing of results with clinicians results in higher rates of guideline-concordant COPD care in those with a positive CAPTURE tool result (CAPTURE+). Study investigators hypothesize that providing CAPTURE screening results to primary care clinicians will increase rates of COPD diagnosis and increase guideline concordant COPD care.

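### SAP section 10 reports between-arm baseline p-values from tests that treat patients as independent, although practices are randomised

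*SAP*

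**What the plan says.** SAP section 10 (Summary of Study Conduct Data) sets out the baseline tables: "Descriptive summary statistics will be tabulated for baseline patient demographics and clinical characteristics as well as practice characteristics, separately by intervention group and overall". For continuous variables, p-values from two-sample t-tests "comparing mean differences between intervention groups will be reported". For categorical variables it names Pearson's chi-square or "Exact test for testing association between categorical predictors and intervention groups, as appropriate, will be given". Section 10 mentions no adjustment for practice, and no other section supplies one for the baseline tables.

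The design is clustered. SAP section 4.1 states: "Randomization to one of two interventions takes place at the practice level". SAP section 7.3 adds that allocation is 1:1, stratified by PBRN, and made when the site is activated. SAP section 8.2 plans 50 practices per arm with 50 patients each.

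The SAP does handle clustering for the primary endpoint. Section 11.1 uses a GEE with practice as the cluster and an exchangeable correlation.

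**The concern.** Patients in one practice tend to resemble each other in insurance, race, education and similar characteristics. When whole practices are allocated, that resemblance widens the chance difference between arms. A patient-level t, chi-square or Fisher test leaves this out, so its standard error is too small and it rejects more often than its nominal level when nothing but chance is at work.

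The baseline table matters more here than in an individually randomised trial. Practices are randomised at activation. Patients are then invited from among those whose clinicians have completed the required education (SAP section 6.1), and only participants are described as blinded to arm, apart from the withholding of CAPTURE results from control practitioners (SAP section 7.3). Recruitment therefore follows allocation, and readers will look to the baseline table for signs of differential recruitment. Unadjusted p-values could make ordinary cluster-level chance look like such bias.

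**Working it through.** **Inputs from the documents**
- 50 practices per arm and 50 patients per practice (SAP 8.2).
- CAPTURE+ patients per practice: 5 by design (SAP 8.2), 10 in the 2020 power memo (SAP 13.1).
- ICC of 0.05, 0.10 and 0.15, given for the composite outcome only (SAP 8.2).
- Stratification by PBRN (SAP 7.3).

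**Assumptions**
- The ICC of baseline variables is not given. I use 0.01 to 0.10: the lower values are assumed and the upper ones borrowed from the outcome.
- The SAP sets no threshold for baseline p-values. I use two-sided 5%.
- The share of the ICC lying between PBRNs is not given. I show 0, 50% and 75%.

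**Step 1: reproduce the plan's own cluster calculation.** The documents give no figure for the baseline tests. The power table is where they use these cluster inputs, so it tests the design-effect formula. Effective n per arm = 44 × 5 / (1 + 4 × ICC). At ICC 0.05 this is 220 / 1.20 = 183.3. A two-sided 5% comparison of two proportions, with 5% in the control arm, gives:

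| ICC | +7.5% computed (stated) | +10% computed (stated) | +15% computed (stated) |
|---|---|---|---|
| 0.05 | 0.721 (0.72) | 0.894 (0.89) | 0.993 (0.99) |
| 0.10 | 0.654 (0.65) | 0.843 (0.84) | 0.983 (0.98) |
| 0.15 | 0.596 (0.59) | 0.793 (0.79) | 0.968 (0.97) |

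The table reproduces, so the plan's own arithmetic uses the design effect DE = 1 + (m − 1) × ICC.

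**Step 2: rejection rate of the unadjusted patient-level test, ignoring strata.** Rate = 2 × [1 − Φ(1.96 / √DE)]. For m = 50 and ICC 0.05, DE = 1 + 49 × 0.05 = 3.45, √DE = 1.857, 1.96 / 1.857 = 1.055, and the rate is 29.1%.

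| ICC | m = 50 (all enrolled) | m = 10 (CAPTURE+) | m = 5 (CAPTURE+) |
|---|---|---|---|
| 0.01 | 10.8% | 6.0% | 5.5% |
| 0.02 | 16.4% | 7.1% | 5.9% |
| 0.05 | 29.1% | 10.4% | 7.4% |
| 0.10 | 42.0% | 15.5% | 9.8% |

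A simulation without strata (4000 runs, 50 practices per arm) agreed within about 1.5 points for both the t-test and the chi-square test. In the same runs a t-test on practice means rejected in 4.4% to 5.8% of null comparisons.

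**Step 3: allow for stratification by PBRN.** Stratified allocation roughly balances between-PBRN variation across arms, so only the within-PBRN part of the ICC adds noise: DE = (1 − ICC) + m × ICC_within. For m = 50, ICC 0.05 and half of it between PBRNs, DE = 0.95 + 50 × 0.025 = 2.20 and the rate is 18.6%.

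| ICC (m = 50) | Between-PBRN share 0 | 50% | 75% |
|---|---|---|---|
| 0.05 | 29% | 19% | 12% |
| 0.10 | 42% | 29% | 18% |

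A simulation with 7 strata of 14 practices gave 30%, 19% and 11% at ICC 0.05, and 41%, 29% and 19% at ICC 0.10.

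**Step 4: does any planned inference use these p-values?** The primary model has the intervention as its only covariate (SAP 11.1). Multivariable models select terms on GEE robust-variance significance (SAP 11.2). Additional imputation predictors are chosen from data pooled across arms (SAP 9.5). None of these draws on the section 10 p-values.

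**The case against.** The strongest reply is that nothing depends on these p-values. They sit in a descriptive section, beside means, standard deviations and percentages that readers can judge for themselves. They choose no covariate, population or conclusion. This stands, and it confines the point to reporting.

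The size is also uncertain. The ICC range is assumed, and the PBRNs were chosen for geographic, socioeconomic and racial or ethnic spread (SAP 6.1), so part of the clustering may lie between PBRNs and be balanced by the stratification. This stands too: the step 2 figures are upper values for each ICC, although inflation remains in step 3.

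A reader might infer that imbalance will be flagged far too often in every baseline table. The documents do not support that. The large rates belong to by-arm tables of all enrolled patients. In the CAPTURE+ primary population, at the design size of 5 per practice, the rate is 5.5-10% even before stratification is counted. SAP section 10.3 also gives its main baseline table columns for CAPTURE status and overall, not for arm. That does not cancel section 10's commitment to by-arm p-values, but it may limit where they appear.

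A reader might also infer that every baseline test is invalid. Location, practice type, residency program, size and in-house spirometry have one value per practice, and ordinary tests on practices are sound for them.

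Finally, these tests over-flag differences. They would not hide recruitment bias, though they make it harder to tell from chance.

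**Conclusion.** The point holds for patient-level baseline variables compared between arms, and only there. At an assumed ICC of 0.01 to 0.10, with PBRN strata ignored, a nominal 5% test would reject in about 11-42% of null comparisons in all-enrolled tables, about 6-16% in CAPTURE+ tables at 10 per practice, and about 5.5-10% at 5 per practice. Stratification lowers these by an amount the documents do not let one fix.

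It would be wrong to conclude that the trial's efficacy result is at risk: the primary GEE accounts for practice and takes nothing from the baseline tests. The harm is a column of misleading p-values in a table that readers will use to look for post-randomisation recruitment bias. It is worth correcting because correction is nearly free.

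**What to change.** In SAP section 10, for patient-level variables, choose one of two wordings.

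- Drop the between-arm p-values and report descriptive statistics by arm, with standardised differences if wanted. These do not remove chance imbalance between clusters, so they still need cautious reading.
- Keep the p-values, but compute them from a GEE or mixed model with practice as the cluster, accounting for PBRN strata.

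In either case, keep ordinary t, chi-square and Fisher tests only for practice-level characteristics, with the practice as the unit. It would also help to state how section 10's by-arm layout fits with the CAPTURE-status columns in section 10.3.

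The cost is one or two sentences of SAP text. No new data are needed and the primary analysis does not change.
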